12.2 Sample Size

We use pilot trials to introduce new technologies, test system component interoperability, and support regulatory approval of larger subsequent studies. Depending on the traceability of the system to previous established technology or components, the pilots can range from a small 5-person 3-day trial, such as the one we used to enable the pivotal trial of Control-IQ, to a multi-center test of pump configurations. This study is directly traceable to the studies described in IDE #G230052 (Neural Net Artificial Pancreas, NAP) and IDE #G240236 (AIDANET), in terms of algorithm functionality – as noted above, the new element is the replacement of the AIDANET built in bolus priming with a new BPS_RL. Thus, based on our experience, we estimate that the completion of N=15 (and recruitment of up to 20) AID system users, will be feasible in terms of first regulatory approval of the new BPS_RL, and sufficient to assess the effect size of the transitions between the existing AIDANET and the new AIDANET+BPS_RL.

The overall aim is to achieve effect size $f = 0.2$ on the primary outcome described below. If this effect size is confirmed, then a subsequent larger study, which is planned within the scope of the NIH/NIDDK Grant RO1 DK 133148 supporting this pilot, will need a sample size of N=50 completed participants to establish superiority of the new AIDANET+BPS_RL over its current version.

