Study Design	A randomized cross-over trial assessing glycemic control on AIDANET+ BPS_RL, compared to the original AIDANET algorithm, which includes two sessions studied in a supervised hotel setting: 1) using AIDANET+ BPS_RL, and 2) using the original AIDANET without modifications including the previous BPS (see IDE G240236).
Number of Sites	1
Endpoint	The primary outcome will be time in range 70-180 mg/dL for an 18-hour period, 6 PM to 12 PM on the next day, including dinner and breakfast meals.
Population	Key Inclusion Criteria: 
 • Age ≥ 18 years of age • Clinical diagnosis, based on investigator assessment, of Type 1 Diabetes for at least 1 year • Currently using insulin for at least six months. • Having used an AID system equipped with Dexcom G6 or G7 sensor within the last 3 months
Sample Size	Complete 16 participants
Treatment Groups	Randomized crossover: Participants will be randomized to two groups differing by the order of controller use: Group A: AIDANET first followed by AIDANET+ BPS_RL; Group B: AIDANET+ BPS_RL followed by AIDANET.
Participant Duration	Approximately 3 weeks, including: 1 week of remotely monitored AIDANET at home for all participants, 3 days/2 nights AIDANET vs. AIDANET+ BPS_RL crossover at a hotel, and 1 week at home remote monitored AIDANET+ BPS_RL for all participants (Figure 1).
Protocol Overview/Synopsis	Following enrollment, 1 week of AIDANET data will be collected and will be used to establish a baseline and initialize the control algorithm. Participants will be then studied at a hotel for approximately 40 hours, including two 18-hour experiments, randomly receiving either AIDANET or AIDANET+ BPS_RL. Participants will then receive the opposite intervention sequentially during the same hotel session and will then transition to 1-week remote monitored home use of AIDANET+ BPS_RL (Figure 1).

TABLE 1. SCHEDULE OF STUDY VISITS AND PROCEDURES

	Screening	AIDANET Training	AIDANET At-Home	Pre-Hotel Check-in Visit	Hotel Session 1	Hotel Session 2	AIDANET+ BPS_RL At-Home	Post-Study Check-in Visit
Location	Clinic/ Remote	Clinic	Home	Remote	Hotel	Hotel	Home	Remote
Visit	1	2	3	4	5	6	7	8
Day	1	2	3-10	10	11-13		14-21	22
Informed Consent	X							
Eligibility Assessment	X							
Medical History	X							
HbA1c		X						
Pregnancy test (if applicable)	X							
Physical Exam	X							
Vital Signs (height/weight)	X				X			
Demographic Survey	X							

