2.3 Study Design

This study is a randomized cross-over trial comparing AIDANET (including the current BPS) to AIDANET+ BPS_RL which includes the new BPS_RL (Figure 1). A week of AIDANET control at home will be followed by a two-night hotel session when participants will cross over from AIDANET to AIDANET+ BPS_RL and vice versa and will use new BPS_RL for a subsequent AIDANET+ BPS_RL week at home. For the majority of time, the participants will not announce meal ingestion to the system, thereby using the system in FCL mode of operation. However, the AIDANET system is designed to also work in hybrid closed-loop (HCL) mode with carbohydrate announcement, if requested by the user; thus, users will be allowed to enter carbohydrate amounts, which will be recorded by the system.

AIDANET+BPS_RL Study Timeline

Completion goal **N=16** subjects

Figure 1: Study Design

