3.2 Participant Recruitment and Enrollment

We will enroll up to 24 participants who have been diagnosed with T1D for at least one year. This enrollment number accounts for dropouts or screen failures that may occur. The goal is to complete a total of approximately 16 participants.

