386 If an exclusionary condition is identified, the study participant will be excluded from participation
387 with follow up and referral to their primary care physician as needed.

388 If the study participant is pregnant, the study physician will discuss the results of the blood test
389 with the participant and the participant will be asked to seek confirmation of the test and the
390 appropriate medical care.

391 Participants who screen-fail or dropout will be replaced if it occurs prior to the Hotel Admission.
392 Screen failed participants may be re-screened if their clinical situation changes as determined by
393 the study physician.

394 **3.8 Personal Equipment Downloads**

395 Up to 6 months of historical data from the participant's personal insulin pump, glucometer, or
396 continuous glucose monitor may be downloaded or recorded. Data will be obtained from the
397 participant's personal insulin pump, glucometer and CGM. This data may be obtained through the
398 commercial applications (e.g., Source, Tidepool, and Dexcom).

399 **3.9 Surveys**

400 Participants will be asked to complete the Demographic Data Survey, INSPIRE Survey, and
401 Technology Expectations Survey as described in section 8.2 prior to using AIDANET equipment.

402 **3.10 Other Considerations**

403 This study is not meant to find out if the participant has any other disease or problem. The study
404 leaders will alert the participant if any of the research results are important to the participant's
405 health during the study. The participant may have a copy of the screening tests to discuss with the
406 personal physician. If blood tests are completed, any blood left over will be thrown away. It will
407 not be stored for any future testing.

408 **3.11 Randomization**

409 Once eligibility is met and screening procedures are completed, the participant will proceed to
410 Randomization. Participants will be randomized 1:1 to one of two groups:

411 **GROUP A:** AIDANET followed by AIDANET+ BPS_RL during the hotel session

412 **GROUP B:** AIDANET+ BPS_RL followed by AIDANET during the hotel session

413 Randomization will occur via REDCap module.

Chapter 4: Study Devices & Training Visit

Visit 2

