An HbA1c value for the participant will be collected prior to the start of the DiAs system. This can be a point-of-care value, lab value, or historical value from within 4 weeks of signing consent. Participants will be asked to place a new sensor 24-72 hours prior to the start of the Visit 2 to allow time for the CGM to warm-up prior to DiAs initialization. The study system is designed to enable full closed loop control and consists of the following elements: the diabetes assistant (DiAs) prototyping platform (smart phone), connected to a Tandem t:AP research insulin pump and a Dexcom G6 CGM.

Participants will come to the research center for initiation and training on the study device as described in Section 4.1. This will consist of 4-8 hours of training, tailored to the individual and include a supervised meal/snack. The participant will be asked to have an active Dexcom G6 sensor by the start of Visit 2; otherwise, a new CGM sensor will be placed. The study team will perform vital signs and inquire about any changes to the participant's medical history. Any changes to medical history will be communicated to the medical physician to ensure continued eligibility and participation.

The participant's CGM reading, and ketone concentration will be recorded. In the event that the participant's CGM reading is not between 80-250 mg/dL or ketone concentration is ≥ 0.6 mmol/L prior to initiation of the FCL system, the study physician may recommend additional insulin dosing according to the participants' usual doses. Study physician may elect to cancel participant's participation in the study if concerned about their medical safety. This participant will not be replaced.

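### The sample size is stated two ways (15 completers of up to 20 recruited; 16 completers of up to 24 enrolled), and the Visit 2 replacement rule does not agree with section 3.7

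*Combined protocol and SAP*

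**What the plan says.** **Completers and ceiling.**
- Section 12.2, the only place that argues for a sample size, judges that "the completion of N=15 (and recruitment of up to 20) AID system users" is feasible and sufficient. The stated basis is experience with earlier pilots.
- The Protocol Summary, Sample Size row, says "Complete 16 participants" and gives no ceiling.
- The Figure 1 text in section 2.3 says "Completion goal N=16 subjects" and gives no ceiling.
- Section 3.2 says "We will enroll up to 24 participants who have been diagnosed with T1D for at least one year", adds that "This enrollment number accounts for dropouts or screen failures that may occur", and continues: "The goal is to complete a total of approximately 16 participants". Section 3.3 counts a person as enrolled once consent is signed.

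**Replacement.**
- Section 3.7: "Participants who screen-fail or dropout will be replaced if it occurs prior to the Hotel Admission".
- Chapter 4 (Visit 2), on a participant whose participation the study physician cancels over medical safety: "This participant will not be replaced".
- Section 6.3 uses the same sentence for a participant cancelled at hotel check-in.
- Section 5.2 lets the investigator cancel an admission after the pre-hotel contact and is silent on replacement.

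**The concern.** The section that justifies the sample size uses a completer target and a ceiling that appear nowhere else. A site following section 3.2 may consent a 21st to 24th participant. Read against section 12.2, the same four people are over the limit. Section 13.3 treats any noncompliance with the protocol as a deviation, so the site cannot tell from the text whether the 21st consent is one. Section 9.2 classes this as a significant-risk device study under an IDE, and the number of people to be exposed should have one value.

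The replacement question affects the same count. Randomization takes place at Visit 1 (Table 1), so a participant cancelled at Visit 2 has already been randomized. Section 3.7 and Chapter 4 appear to give opposite answers on whether that place is filled again.

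**Working it through.** **1. Can the plan's own figure be reproduced?** No. Section 12.2 gives no significance level, power, standard deviation or loss rate for the 15, and section 12.6 says that formal power analysis does not apply. The check is therefore a comparison of texts, followed by a calculation of how much the difference matters.

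**2. The figures side by side.**

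| Place | Completers | Ceiling |
|---|---|---|
| Section 12.2 | 15 | 20 recruited |
| Protocol Summary | 16 | not given |
| Figure 1 text, section 2.3 | 16 | not given |
| Section 3.2 | about 16 | 24 enrolled |

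Completers differ by 16 − 15 = 1. Ceilings differ by 24 − 20 = 4, which is 4/20 = 20% of the lower one. The ceiling conflict is between one section and one other section, because only section 3.2 gives 24.

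**3. Implied allowance for loss.** Section 12.2: (20 − 15)/20 = 25.0%. Section 3.2: (24 − 16)/24 = 33.3%. At a 25% loss, 16 completers would need 16/0.75 = 21.3, so 22. No loss rate is stated that would favour either ceiling. The two percentages are comparable only if recruited and enrolled count the same people.

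**4. What one completer is worth.** Take f = 0.2 from section 12.2 and a repeated-measures F test with two measurements per person:

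λ = f² × N × 2/(1 − ρ), on 1 and N − 1 degrees of freedom.

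Two inputs are assumptions not found in the protocol: two-sided α = 0.05, and within-person correlation ρ = 0.5 (range 0 to 0.8). At ρ = 0.5:
- N = 15: λ = 0.04 × 15 × 4 = 2.40, power 30.3%
- N = 16: λ = 0.04 × 16 × 4 = 2.56, power 32.2%

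| ρ | Power, N = 15 | Power, N = 16 |
|---|---|---|
| 0 | 17.5% | 18.5% |
| 0.3 | 23.1% | 24.5% |
| 0.5 | 30.3% | 32.2% |
| 0.7 | 46.1% | 48.9% |
| 0.8 | 62.5% | 65.8% |

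As a check on the assumptions, N = 50 for the later study gives λ = 8.0 and power 79.2% at ρ = 0.5, with 52 needed for 80%. The section 12.2 figure of 50 is thus consistent with ρ = 0.5, though the protocol does not say it was derived that way. The section 12.6 statement that power is below 50% holds for both 15 and 16 up to ρ of about 0.7.

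Precision: the 95% half-width for the mean paired difference is t(0.975, N − 1)/√N, in units of the SD of the differences. This is 0.55 at N = 15 and 0.53 at N = 16.

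**5. Replacement.** Table 1 puts Visit 2 on Day 2 and the hotel on Days 11–13. A physician cancellation at Visit 2 therefore precedes hotel admission. If it counts as a dropout, section 3.7 replaces that participant and Chapter 4 does not. Section 6.3 can be squared with section 3.7 if arrival at check-in counts as admission. The conflict is between section 3.7 and Chapter 4.

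**The case against.** **The targets nearly agree.** Section 3.2 says approximately 16, which can cover 15, and both ceilings are upper limits. This stands as far as completers go, and step 4 shows the difference has little statistical weight. It does not cover 20 against 24.

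**Recruited may not mean enrolled.** Section 12.2 does not define recruitment or say whether its 20 includes screen failures, whereas the 24 counts signed consents and does include them. On a narrower meaning of recruited, the two ceilings could coexist. The protocol does not draw that distinction, and it would not explain 15 against 16.

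**Chapter 4 may be an exception.** Section 3.7 speaks of screen failure and dropout, and Chapter 4 speaks of a physician's cancellation. Dropout is not defined, so a general rule with a specific exception is a possible reading. This stands as a possibility, but neither section refers to the other or states an exception.

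**Stronger readings that the protocol does not support.**
- A reader might infer that the target sample size is undefined. It is defined twice, one completer apart, so this is an inconsistency and not a sizing failure.
- A reader might object that 15 is odd and cannot be split 1:1. The 1:1 ratio in section 3.11 applies to those randomized, not to completers. Section 12.1 uses Bernoulli trials with an aim to balance HbA1c, so 16 completers would not be guaranteed to fall 8 and 8 either.
- A reader might infer that an unblinded team could pick between the two numbers after seeing data. Staff can see CGM data in real time, but the protocol does not state the blinding status of those who close enrolment, and nothing in it indicates such a choice.

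**Conclusion.** The inconsistency is real and should be corrected. Section 12.2 gives 15 completers of up to 20 recruited. Three other places give 16 completers, and one of these gives a ceiling of 24 enrolled. The completer difference moves power at f = 0.2 by about 2 percentage points at the assumed ρ = 0.5, and by 1 to 3.3 points over ρ from 0 to 0.8. It does not change what the pilot can show. The practical part is the ceiling, where the status of participants 21 to 24 depends on which section is read, provided recruited and enrolled mean the same people.

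The replacement statements in section 3.7 and Chapter 4 conflict as written for a participant cancelled at Visit 2, unless Chapter 4 is an unstated exception. The textual findings need no assumption about correlation or significance level; only the power figures do.

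**What to change.** 1. In section 12.2, replace 15 and 20 with the figures used elsewhere: 16 completers and up to 24 enrolled. Use the section 3.3 meaning of enrolled, so that one completer target and one ceiling, counting the same people, appear throughout. The experience-based argument in section 12.2 does not depend on 15 rather than 16.
2. State the loss allowance behind the ceiling (8 of 24, or 33.3%, covering screen failures and dropouts).
3. Merge section 3.7 and the Chapter 4 sentence into one replacement rule. If a cancellation at Visit 2 is meant as an exception, say so in both places. Which rule to keep is the sponsor's choice. The same edit can say whether section 6.3 check-in counts as after admission and how a section 5.2 cancellation is treated.

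The cost is protocol wording only. No procedure, analysis or randomization method has to change.

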12.3 Outcome Measures

The primary outcome will be the CGM-measured time in range (TIR, 70-180 mg/dL) during the 18-hour hotel sessions on AIDANET or AIDANET+BPS_RL (Figure 1). The time periods begin at 6 PM and end at noon on the next day, thereby covering two meals – dinner and breakfast. These

time periods are expected to reflect well any differences, e.g., potential TIR improvement, that can be attributed to the new BPS_RL.

Secondary outcomes from the 18-hour Hotel Sessions of the study (see Figure 1):

Descriptive glycemic analyses for certain efficacy measures recommended by the International Consensus on TIR, to which we contributed, will be tabulated for each subject based on CGM data, including:

- percentage of readings in other ranges, including time below range (TBR, < 70 mg/dl), time above range (TAR, > 180 mg/dl) and time in tight range 70-140 mg/dl;
- mean glucose; glucose variability measured by coefficient of variation;
- percentage of readings <54 mg/dl (i.e., level 2 hypoglycemia)
- percentage of readings >250 and >300 mg/dl (i.e., level 2 hyperglycemia).

Secondary outcomes from the 1-week Home Sessions of the study (see Figure 1):

All CGM-based glycemic metrics computed during the Hotel sessions of the study will be computed during the Home sessions as well. *The last 3 days of each week at home on AIDANET or AIDANET+BPS_RL will be used for the analyses described below.*

We will also observe, record, and tabulate any system errors that would inform us whether system fixes would be needed prior to deployment in a subsequent larger study. We will tabulate technical performance metrics including:

- Malfunctions requiring study team contact and other reported device issues;
- Percent time in closed-loop and any other relevant operational modes;
- Rate of relevant AIDANET+BPS_RL failure events and alarms per 24 hours;

The technical performance, errors, and glycemic analyses will be also split by time of the day: daytime vs. night-time.

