The second step was a further optimization of the neural network structure and size. This was completed in the summer of 2024 and IDE #G240236 was submitted to the FDA, with the objective to conduct a trial validating the optimized AIDANET (Automated insulin delivery as Adaptive Network) system during a 2-night house/hotel session and during 1 week at home. This IDE was approved on 10 Oct 2024 and the AIDANET trial is anticipated to be completed by the end of 2024 (NCT06633965). Participants use the AIDANET system in fully automated closed-loop (FCL) mode, with the exception of using their insulin-to-carbohydrate ratio as usual during 1 dinner in the house/hotel session of the study and 1 day at home and announcing eating initiation for 1 day at home. This study also includes a 1-week control period gathering data on glycemic control and insulin administration with the participants’ usual care therapy. Participants are randomized 1:1 to either Group A (control period prior to AIDANET use) or Group B (control period after AIDANET use).

Following Steps 1 and 2 described above, we developed a new version of the AIDANET bolus priming system (BPS) that uses reinforcement learning to determine pre-meal bolus amounts. Reinforcement learning (RL) is a branch of machine learning where an agent, like a neural network, learns to make decisions by interacting with its environment. Through trial and error, the agent receives feedback (rewards or penalties) for its actions, allowing it to refine its strategy over

time and maximize the total reward. By training our BPS using RL in an FDA-approved virtual environment, we developed a pre-meal bolus strategy optimized at the population level, meaning it works effectively for all patients. This updated BPS-RL is also able to analyze three days of glucose and insulin data to identify patterns and optimize the priming bolus, whereas the current BPS only uses the last 30 minutes of data. Moving forward, the RL-based system will allow for further personalization using patient-specific data in future research studies.

This protocol is the third step in the development of the next-generation AID algorithms that begin to use machine learning to adapt to the changing state of the person wearing the AID system. The goal of the protocol is to assess whether AIDANET plus reinforcement learning trained BPS (AIDANET+ BPS_RL) continues to provide safe and effective glycemia management as seen in prior studies.

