2.2 Specific Aims and Hypotheses

Aim 1: To evaluate the performance (safety, efficacy) of AIDANET+ BPS_RL used as FCL.

Hypothesis: AIDANET+ BPS_RL use will result in equivalent or better Time in Range (TIR) than AIDANET (including current BPS) during two 18-hour hotel sessions (randomized crossover).

[figure not shown]
Aim 2: To evaluate the safety and efficacy of AIDANET+ BPS_RL at home.

Hypothesis: AIDANET+ BPS_RL use will result in equivalent or better TIR than AIDANET alone, during a week of At-Home use (repeated measures).

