4.1 Insulin Pump and DiAs

4.1.1 Equipment Description.

A study insulin pump and DiAs will be provided to all participants at this training visit.

The t:AP research insulin pump will be programmed with the participants' usual pump parameters (basal insulin rate, insulin to carbohydrate ratio, and insulin correction factor) as determined by the study physician. These parameters serve as backup-only settings for the system in open loop mode, and do not determine behavior of the AIDANET algorithm. The bolus priming system (BPS) profile determines the maximum fraction of total daily insulin (TDI) that can be injected by the BPS depending on the time of day (e.g., 8% between 06:00 and 10:00). The BPS profile is a setting on DiAs which can be modified by the provider to impact performance of the AIDANET algorithm. The study physician may alter the BPS profile during the hotel session and At-Home portions of the study to optimize participant safety with the experimental system.

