7.1 AIDANET+BPS_RL use at home

Upon discharge on Day 3 of the hotel period, participants will begin a 7-day/6-night Remote Monitored At-Home stage of the study. Participants will continue to wear the FCL research system as initiated during the hotel period. Participants will be instructed to eat approximately 3 freely chosen meals per day without announcing them to the system. Participants will be instructed to participate in their usual level of physical activity. Participants will complete the study after lunch on overall study Day 9 (Day 7 of the home portion), at which point they will return to use of their usual diabetes care.

Approximately 24-48 hours after initiating the system, the study team will contact the participant via phone/email/text/video to assess adverse events, adverse device effects, and device issues. If the participant chooses, this visit can occur at the clinical site. The study team will verify the following information:

1. Review system use
2. Inquire about any changes to the participant's medical history
3. Inquire about any changes to the participant's medication
4. Review of CGM data
5. Review of hypoglycemic events
6. Review of hyperglycemic events

Any other relevant contacts during the week will be recorded on the CRF and summarized as appropriate (e.g. contact that is not a scheduling or supplies issue will not be recorded).

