12.4 Planned Analysis

The primary statistical effect of interest is the change in TIR resulting from the transition from AIDANET to AIDANET+BPS_RL and vice versa. Thus, the analysis will involve use of repeated measures General Linear Model (GLM), with emphasis on the interaction corresponding to the crossover design. The analysis will use covariates, e.g., baseline HbA1c, gender, and TIR within the first week on AIDANET alone (see Figure 1).

All secondary outcomes will be similarly analyzed. In particular, the CGM-based metrics of the last 3 days on AIDANET will be compared to the last 3 days on AIDANET+BPS_RL using repeated measures CLM with covariates as described above. If the distribution of an outcome is not suited for GLM (e.g., profound skewness, or atom at boundary), we will perform paired Wilcoxon signed rank test (and lose the capacity to use covariates) to test difference in the median instead of the mean; this is expected for time < 54 mg/dl and possibly time >250 and 300 mg/dL.

We do not plan to correct for multiple comparisons. We do not expect substantial missing values in this supervised study, but if more than 20% of the data for the primary outcome is missing, we will consider switching to mixed models that handle missing data better.

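### The home CGM comparison, hypoglycaemia included, uses only the last 3 days of each week, so CGM-measured lows on the first home days with BPS_RL have no specified analysis

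*Combined protocol and SAP*

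**What the plan says.** Section 2.2 sets the question: "Aim 2: To evaluate the safety and efficacy of AIDANET+ BPS_RL at home". The hypothesis beneath it concerns TIR and refers to a week of home use.

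Section 12.3 carries the hotel metrics over to the home periods: "All CGM-based glycemic metrics computed during the Hotel sessions of the study will be computed during the Home sessions as well". That set includes "time below range (TBR, < 70 mg/dl") as well as readings below 54, above 250 and above 300 mg/dL. The next sentence sets the window: the "last 3 days of each week at home on AIDANET or AIDANET+BPS_RL will be used for the analyses described below". Section 12.4 applies it: "the CGM-based metrics of the last 3 days on AIDANET will be compared to the last 3 days on AIDANET+BPS_RL". Neither section exempts the hypoglycaemia metrics, and neither gives a reason for the window.

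On the length of the period, Section 7.1 says that "participants will begin a 7-day/6-night Remote Monitored At-Home stage of the study". Section 5.1 gives the AIDANET week the same length.

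On changes during use, Section 4.1.1 says: "The study physician may alter the BPS profile during the hotel session and At-Home portions of the study to optimize participant safety". Section 4.1.2 also allows pump or system settings to be optimised at any time, with recurring hypo- or hyperglycaemia as the named trigger.

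**The concern.** A window that opens late in the week suits an efficacy question. Chapter 1 describes BPS_RL as able "to analyze three days of glucose and insulin data to identify patterns and optimize the priming bolus", so for roughly the first three home days its data history reaches back to the hotel stay. Part of that stay was spent on AIDANET, and for Group B it was the part just before going home. The plan does not offer this reason, but it is a sensible one for TIR.

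It does not carry over to safety. Anyone who starts BPS_RL passes through the start-up days, so lows on those days are part of what Aim 2 asks about. Two mechanisms could also make the last 3 days look better than the week as a whole:

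- Early lows may prompt a BPS profile or settings change before the window opens.
- A participant who stops in the first days has no last-3-days value. Section 11.2 leaves the use of withdrawn participants' data to the study team, and Section 3.7 provides for replacement only before hotel admission.

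At stake is whether the home safety result describes the whole period of use or only its settled part.

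**Working it through.** The plan gives no figure of its own on this point, so there is nothing to reproduce.

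**1. Share of the home period analysed.**

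Inputs: the 3-day window (12.3, 12.4); 7 days and 6 nights at home (5.1, 7.1); for the BPS_RL week, start after lunch at hotel discharge (6.7) and end after lunch on home day 7 (7.1); completion goal of 16 (3.2).

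- By hours: 6 × 24 = 144 h. Taking 3 days as 72 h, 72/144 = 50% is kept and 50% set aside. At N = 16 that is 16 × 72/24 = 48 of 16 × 144/24 = 96 person-days set aside.
- By calendar days: 3/7 = 43% is kept and 4/7 = 57% set aside. At N = 16 that is 64 of 112 person-days set aside.

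**2. Where a low on an early BPS_RL home day would be reported.**

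| Place in the plan | Covers early home days? | Covers non-severe CGM lows? |
|---|---|---|
| 12.3 and 12.4, home CGM comparison | No, last 3 days only | Yes, below 70 and below 54 mg/dL |
| 10.2 and 10.2.1, reportable events | Yes | Generally no, unless tied to an adverse device effect |
| 12.5, safety analyses | No period stated | Names lows below 70 mg/dL, but no metric |
| 12.6, TBR criterion | No period stated | Yes, difference under 3 percentage points |
| 7.1 contact at 24–48 h and 7.2 alerts | Yes | Reviewed or acted on; no exposure-based summary specified |

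No row specifies an analysis of CGM time below 70 or 54 mg/dL on the early home days.

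**3. How far the 3-day and whole-week results can differ.**

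The documents give no TBR values, so these figures are assumptions for illustration only. Let E be the TBR difference (BPS_RL minus AIDANET) on the early days and L the difference on the last 3 days.

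- Calendar-day weighting: whole-week difference = (4E + 3L)/7.
- Hour weighting: whole-week difference = (72E + 72L)/144 = (E + L)/2.

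With L = 0, the 3-day analysis shows 0 in every row:

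| E (points) | Whole week, 4:3 | Whole week, 1:1 |
|---|---|---|
| 1 | 0.57 | 0.50 |
| 3 | 1.71 | 1.50 |
| 5 | 2.86 | 2.50 |
| 7 | 4.00 | 3.50 |

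A whole-week difference of 3 points needs E = 3 × 7/4 = 5.25 points with 4:3 weighting, or 3 × 2 = 6 points with equal weighting. Smaller early excesses stay below 3 points over the week, but the 3-day analysis would not show them either.

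**The case against.** The strongest reply is that the early days are watched and that serious harm is counted. Remote monitoring runs in both home weeks (2.5, 7.2), with provider alerts for CGM below 70 mg/dL for 20 minutes or below 55 at any point. Section 7.1 adds a contact 24–48 hours after the system is initiated, which includes review of hypoglycaemic events. Severe hypoglycaemia, DKA and adverse device effects are reportable, and the stopping criteria apply, with no 3-day limit. Every participant first meets BPS_RL in the staffed hotel session. Section 12.3 introduces the CGM list as efficacy measures, and 12.5 is a separate safety section with no window, which is ambiguity rather than exclusion.

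All of this stands, and it rules out three stronger readings that a reader might infer:

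- *That the early home days are unsupervised, or that their safety data are discarded.* They are remotely monitored, and what lacks an analysis is CGM-measured, mostly non-severe, hypoglycaemia.
- *That the window always favours BPS_RL.* The same window and the same freedom to change settings apply in both weeks. It also drops the first AIDANET days, when participants are new to the study pump, phone and fully closed-loop use.
- *That the window could decide the 3-point TBR criterion.* Section 12.6 does not say that the criterion applies to the home period.

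The reply does not supply an analysis of early time below 70 or 54 mg/dL. Monitoring and alerts protect participants, but they do not produce a prespecified estimate. Symmetry makes the direction of bias uncertain without making the early days visible.

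**Conclusion.** The point holds as a gap in the home safety analysis. Sections 12.3 and 12.4 state a rule that leaves half of each home period (72 of 144 h; 4 of 7 by calendar days) out of the CGM comparison, and no other section specifies a summary of non-severe lows on those days. The result can understate hypoglycaemia on BPS_RL where early lows lead to a change or to stopping. How often that will happen, and whether the AIDANET week is affected as much, cannot be known from the documents. The exposure share rests on reading 3 days as 72 h and the home week as lunch to lunch; the TBR figures rest on assumed early differences, no late difference and the stated weights.

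The weight is moderate. This is a secondary comparison in a pilot that makes no claim to power, and the primary outcome, hotel TIR, does not use the window. It is a cheap improvement, not a condition for the trial to proceed.

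**What to change.** Keep the last 3 days for TIR and the other efficacy metrics, and give the reason for the run-in. Then, in Sections 12.3 to 12.6:

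1. Prespecify that time below 70, below 54, above 250 and above 300 mg/dL is also summarised over the whole home period on each algorithm, from start to end of use, with the early days shown separately from the last 3 days.
2. Include participants who stop early, using the time they contributed.
3. List BPS profile and settings changes by day and reason for both home weeks.
4. State which period Section 12.5 uses, and which period the TBR criterion in 12.6 uses.

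The cost is SAP wording, one extra table and a short listing. Table 2 already plans CGM capture in both home periods, so the glucose summaries need no new data. The downside is that home TBR may look less favourable. The change should be made before the home data are reviewed, so that the whole-period summary is prespecified.
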